5.5 Subject Withdrawal

5.5.1 *Reasons for Withdrawal*

Subjects are free to withdraw from participation in the study at any time upon request. An investigator may terminate a study subject's participation in the study if:

- Any clinical adverse event (AE), laboratory abnormality, or other medical condition or situation occurs such that continued participation in the study would not be in the best interest of the subject.
- The subject meets an exclusion criterion (either newly developed or not previously recognized) that precludes further study participation.

5.5.2 *Handling of Subject Withdrawals or Subject Discontinuation of Study Intervention*

Subjects wishing to withdraw from the study at any time may do so and should notify the study team. For payment to these subjects, see Section 5.3.

Withdrawals need not be replaced, but may be on a case-by-case basis, at the PI's discretion. The power calculations allow for a 20% dropout rate.

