7.2 TMD Patients

Prescreening (Study Week -8)

Chronic TMD subjects interested in the study will be prescreened via a phone interview using an IRB-approved checklist.

Screening
(*Study Week -3*)

The activities assigned to the Screening Visit will be completed within 3 weeks prior to the first session of Week 1. Following the informed consent process, subjects will undergo a baseline assessment and the completion of questionnaires, as listed in the study schedule (Table 2). The baseline visit will include a medical/dental history with limited physical that involves clinician assessed DC/TMD (Diagnostic Criteria/Temporomandibular Disorder) status. Also covered are a comprehensive medication history (6 months) and a review of eligibility.

Baseline PET/MRI
(*Study Week -1*)

Within 7 days preceding randomization and the first study treatment, subjects will undergo an MRI, as well as a PET scan that uses an [¹¹C]carfentanil radioligand, with a masseter muscle pain challenge via a 5% hypertonic saline intramuscular infusion. Pain questionnaires will also be completed during this visit window. All procedures are targeted for the week prior to HD-tDCS; however, due to occasional scheduling difficulties, they may be completed within 14 days prior to Day 1 of HD-tDCS. Completion of all procedures may require more than one clinic visit.

Treatment HD-tDCS
(*Study Weeks 1 through 2*)

Beginning at Day 1 of HD-tDCS, subjects will be randomized to active treatment or sham procedure. They will then attend 10 sessions, 1 each weekday (Monday through Friday) over a 2-week period, and will receive either the M1 HD-tDCS treatment or the sham treatment, preceded and followed by questionnaires. Missed days can be doubled and/or rescheduled within the 2-week schedule, as necessary, with study team approval.

Follow-up PET
Follow-up MRI &
First Follow-up Visit
(*Study Week 3*)

Within 7 days following the last study treatment, subjects will undergo an MRI as well as a PET scan that uses an [¹¹C]carfentanil radioligand with a masseter muscle pain challenge via a 5% hypertonic saline intramuscular infusion. Pain questionnaires will also be completed during this visit window. All procedures are targeted for the week following completion of HD-tDCS; however, due to occasional scheduling difficulties, they may be completed within 14 days following Day 10 of HD-tDCS. Completion of all procedures may require more than one clinic visit.

Follow-Up #2 & #3
(Study Weeks 6 and 10)

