Pain questionnaires will be completed again at 4 weeks (Follow-Up #2) and 8 weeks (Follow-Up #3) after the final treatment day (Study Weeks 6 and 10, respectively).

Table 2

SCHEDULE OF EVENTS – I. Procedures

Procedures	Phone PreScreening	Screening	PET/MRI #1 (Baseline) ^{1,2}	HD-tDCS #1-10 ⁸	PET/MRI #2/ Follow-up #1 ^{1,2}	Follow-up #2	Follow-up #3	Early Termination ³
Visit	P	1	2	3A-J	4	5	6	ET
Study Week	-8	-3	-1	1 – 2	3	6 (1 mth)	10 (2 mths)	N/A
Prescreening Script/Checklist	X ⁵							
Informed Consent		X ⁵						
Adverse Events		X ⁵	X ⁵	X	X	X	X	X
Medical/Dental History and Physical		X ⁵						
Medication History/ Concomitant Medications		X ⁵	X ⁵	X	X	X	X	
Quantitative Sensory Testing (QST)			X ⁵		X			
Eligibility Assessment ⁴		X ⁵						
PET Scan 
 Pregnancy Test (Dip)⁷ Drug Screen⁷ Blood sample for biomarkers Masseteric Pain Challenge (5% hypertonic saline) 			X ⁵		X			
Blood sample for genetic testing			X ⁵					
MRI Scan			X ⁵		X			
RANDOMIZATION				Week 1				
HD-tDCS (M-F for 2 weeks)				X ⁶				

¹ Target dates for PET/MRI are the week prior to Day 1 HD-tDCS session (Baseline) and the week after completion of HD-tDCS sessions (Follow-up); an additional week window is allowed to account for scheduling issues.

² Procedures may require more than one clinic visit.

³ Applicable if subject completes an in-person visit.

⁴ If subject is deemed eligible, schedule subject visits and provide subject with instructions for PET & MRI.

⁵ Healthy Volunteer subjects complete only these procedures indicated.

⁶ Missed days can be doubled in the (M-F) x 2 schedule, with study team approval. See Section 7.

⁷ Completed within 24 hours prior to PET session

⁸ HD-tDCS sessions will be scheduled M-F. See Section 7.2.

Table 2
SCHEDULE OF EVENTS – II. Questionnaires

Questionnaires	Phone PreScreening	Screening	PET/MRI #1 (Baseline) ^{1,2}	HD-tDCS #1-10 ⁸	PET/MRI #2/ Follow Up#1 ^{1,2}	Follow Up #2	Follow Up #3	Early Termination ³
Visit	P	1	2	3A-J	4	5	6	ET
Study Week	-8	-3	-1	1 – 2	3	6 (1 mth)	10 (2 mths)	N/A
Demographics		X ⁷						
Beck Depression Inventory		X ⁷						
DC/TMD Examination Form		X ⁷				X	X	
Expectation of Effect VAS		X						
McGill Pain Questionnaire (MPQ) (Long Form)		X						
MPQ (Short Form) ⁶		X	X	X	X	X	X	
Positive and Negative Affect Schedule (PANAS) ⁶		X ⁷	X ⁷	X	X	X	X	
GeoPain (via mobile device) ⁶		X	X	X	X	X	X	
Visual Analog Scale (VAS) ⁶		X	X	X	X	X	X	
Graded Chronic Pain Scale		X			X	X	X	

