9.5 Halting Rules

If we see a pattern of worsening in symptoms across patients including severe levels on pain measures, we will halt the study to guarantee the safety of all patients.

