12 STATISTICAL CONSIDERATIONS

Intent-to-treat Population: An intent-to-treat analysis will be performed including all subjects who complete at least 1 set of post-treatment assessments following HD-tDCS treatment for the primary and secondary effectiveness objectives of the study.

Safety Population: Safety measures will be reported for all subjects who receive at least 1 session of sham or active HD-tDCS treatment.

Healthy Volunteers: An analysis will be performed including all subjects who complete 1 set of PET sessions. TMD patients will be compared with healthy controls to test for differences in μ OR BP_{ND} at the baseline level in the thalamus and other pain-related regions.

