12.3.1 Safety Review

Adverse events will be summarized by treatment group and categorized by severity and relationship to study procedures. If a subject has more than one occurrence of the same AE, he/she will be counted only once for that preferred term in the summary tables. The most severe occurrence of an AE and the most extreme relationship of the AE to the study procedures will be indicated in cases of multiple occurrences of the same AE.

The safety of the HD-tDCS procedure will be tested by comparing the proportion of subjects with each solicited AE in the HD-tDCS treatment group and the sham treatment group.

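### The Safety Population in section 12 leaves healthy volunteers, and TMD patients who stop after PET #1, out of the safety summary although both receive the tracer and the saline challenge

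*Combined protocol and SAP*

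**What the plan says.** Section 12 defines the Safety Population by receipt of stimulation: "Safety measures will be reported for all subjects who receive at least 1 session of sham or active HD-tDCS treatment". The Healthy Volunteers paragraph of the same section adds a second set: "An analysis will be performed including all subjects who complete 1 set of PET sessions". Its stated use is a comparison of receptor binding with TMD patients. It mentions no safety reporting, and it is limited to those who complete the scan.

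Section 12.3.1 gives the layout of the summary: "Adverse events will be summarized by treatment group and categorized by severity and relationship to study procedures". Volunteers have no treatment group.

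The exposures are wider than the Safety Population. Section 8.1.2 has the PET scan and saline challenge done twice in each TMD subject and once in each volunteer. Section 2.3 says that all the listed risks except those of HD-tDCS apply to patients and volunteers alike. Section 2.3.3 includes respiratory depression or arrest among the signs of carfentanil exposure.

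Adverse events are collected from everyone. Section 3.2.3 solicits them at each visit after consent. In Table 2 the adverse-event row carries footnote 5 at Screening and PET/MRI #1, and that footnote reads: "Healthy Volunteer subjects complete only these procedures indicated".

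**The concern.** Two groups are exposed to the tracer and the challenge but have no place in the stated safety summary.

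- **Healthy volunteers.** They never have a stimulation session, so none of them can enter the Safety Population. A volunteer who stops mid-scan because of an adverse event is not in the section 12 volunteer set either, because that set requires completion.
- **TMD patients who stop between PET #1 and the first session.** Section 7.2 says of the baseline scans that "they may be completed within 14 days prior to Day 1 of HD-tDCS", and randomization comes only then: "Beginning at Day 1 of HD-tDCS, subjects will be randomized to active treatment or sham procedure". Section 5.5.1 lists as a ground for ending participation: "Any clinical adverse event (AE), laboratory abnormality, or other medical condition or situation occurs such that continued participation". Those who drop out in this interval may therefore include the people who reacted badly to the scan or the challenge.

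At stake is a fair account of what the procedures do to people. Section 2.3.2 says that, preliminary data aside, the center has not used this challenge in TMD patients before. Leaving out patients who stopped after their first challenge could make the procedure look better tolerated than it was. For volunteers, who take on the procedure risk with no prospect of treatment, the plan states no safety summary at all.

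**Working it through.** The plan gives no figure for this point, so there is none to reproduce. The check is a count of who falls inside and outside the stated set.

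**Inputs**
- TMD patients: 60 (section 4), two scans each (8.1.2).
- Healthy volunteers scanned under this protocol (HV): 20 if 10 prior-project controls are used (Protocol Summary, section 4). With up to 12 prior controls (5.3) it is 30 − 12 = 18. With none it is 30. One scan each (8.1.2).
- TMD patients scanned at PET #1 who never have a session (d): not given.

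**Formulas**, with d counted in addition to 60 treated patients who are assumed to complete both scans:
- share of people omitted = (HV + d) / (60 + d + HV)
- share of scans omitted = (HV + d) / (120 + d + HV)

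**Volunteers only (d = 0)**

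| HV | People omitted | Scans omitted |
|---|---|---|
| 18 | 18/78 = 23.1% | 18/138 = 13.0% |
| 20 | 20/80 = 25.0% | 20/140 = 14.3% |
| 30 | 30/90 = 33.3% | 30/150 = 20.0% |

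**Adding early stops (HV = 20).** The values of d are assumptions. They equal 5%, 10% and 20% of 60. The last matches the overall dropout allowance in section 5.5.2, which is not specific to this interval.

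| d | People omitted | Scans omitted |
|---|---|---|
| 3 | 23/83 = 27.7% | 23/143 = 16.1% |
| 6 | 26/86 = 30.2% | 26/146 = 17.8% |
| 12 | 32/92 = 34.8% | 32/152 = 21.1% |

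**Precision.** If a given event is never seen, the one-sided 95% upper bound on its per-subject risk is 1 − 0.05^(1/n). For n = 60 it is 4.9%. For n = 80 it is 3.7%, and for n = 90 it is 3.3%. The gain from 60 to 80 comes from pooling volunteers with patients and assumes a common risk, for which the documents give no basis. For TMD patients alone the bound stays at 4.9% on 60. The reason for the wider set is therefore complete coverage of those exposed, more than a tighter bound.

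**The case against.** The strongest reply is that nothing is lost to oversight. Adverse events are recorded for all subjects from consent (section 7, Table 2). Section 9.4.2 sends every serious event to NIDCR whatever its relationship, within 24 or 72 hours. Unanticipated problems are reported for any subject (9.1.1, 9.4.1), and sections 5.6 and 9.4.3 allow or require stopping for risk to subjects. The center also reports long experience with the tracer and, outside TMD, with the challenge. All of this stands, and it confines the point to the summary of procedure events. It does not supply a summary with a denominator for expected or non-serious events in the omitted groups.

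A second reply is that table detail belongs to the separate SAP to which section 12.4 defers. That SAP is not in the text reviewed and may already cover the matter. This also stands, and it limits confidence.

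Three stronger readings are tempting, and the documents do not support them.

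- *PET #1 events of treated patients are lost.* Section 12 says who is included, not from when events count. A patient who later has one session brings the earlier events along. Listing them under the arm assigned later still reports them, and section 12.3.1 also sorts events by relationship to study procedures.
- *The halting rule excludes volunteers.* Section 9.5 reads: "If we see a pattern of worsening in symptoms across patients including severe levels on pain measures, we will halt the study". The protocol uses the word *patients* loosely elsewhere. Section 2.3.3 states the carfentanil mass limit per patient, although it applies to everyone scanned. One word does not show an intended exclusion.
- *Section 9.5 needs a by-arm review before a halt.* A halt that requires no arm comparison is arguably the more protective rule. Replacing it with a review could weaken it, and section 10 already lets the DSMB meet more often when safety concerns arise.

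**Conclusion.** The concern holds as a gap in the safety summary. As written, section 12 omits every healthy volunteer scanned under this protocol, about 25% of exposed people and 14% of scans (23% to 33% and 13% to 20% for 18 to 30 volunteers), plus any TMD patient who stops after PET #1. These shares assume full enrolment of 60 treated patients with both scans completed. The number of early stops is unknown, and the figures that include them are illustrations only.

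The gap does not reach adverse-event collection, expedited reporting, the PET #1 events of treated patients or the power to stop the study. The documents give no adverse-event rate for the tracer or the challenge and do not support assuming equal risk in volunteers and patients, so no probability of a missed event is claimed. This is an inexpensive improvement to the plan. It lapses if the separate SAP already provides the summary.

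**What to change.** In section 12, add a procedure-safety set: all subjects who receive the tracer or start the saline challenge under this protocol, including those who stop mid-scan or before the first HD-tDCS session. Prior-project controls do not belong in it, since they were not scanned under this protocol. Tabulate tracer and challenge events for this set, with healthy volunteers and TMD patients in separate columns. Keep the existing Safety Population for HD-tDCS events by arm.

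Optionally, change *patients* to *subjects* in section 9.5 for clarity, and leave the rest of that rule as it is.

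The cost is a wording amendment, which needs IRB review and approval under section 15.2, and some extra table columns. It needs no new data, visits or staff. If the separate SAP already covers this, a cross-reference in section 12 is enough.

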12.1 Study Hypotheses

There are 6 hypotheses regarding the outcomes of this study.

12.1.1 *Hypothesis #1*

In chronic TMD subjects, ten daily sessions of active M1 modulation will result in a significant reduction in clinical pain intensity at rest compared to sham treatment, as measured by VAS scores at 4 weeks after completion of the HD-tDCS sessions.

12.1.2 *Hypothesis #2*

Ten daily sessions of M1 HD-tDCS will result in reductions in clinical (at rest) and experimental (sustained masseteric pain stress challenge) pain intensity measures in chronic TMD subjects at the time of the follow-up PET session, 1 week after completion of the HD-tDCS sessions.

12.1.3 *Hypothesis #3*

Ten daily sessions of M1 HD-tDCS will result in significant reductions in clinical pain intensity and area measures in chronic TMD subjects treated with HD-tDCS compared with those treated with a sham treatment over the short and long terms, measured by GeoPain.

12.1.4 *Hypothesis #4*

Ten daily sessions of M1 HD-tDCS will result in an increase of μ OR BP_{ND} in the thalamus and/or other pain-related regions in the brains of chronic TMD subjects from the baseline PET (#1) session to the follow-up PET (#2) session, 1 week after completion of HD-tDCS sessions.

12.1.5 *Hypothesis #5*

Ten daily sessions of M1 HD-tDCS will result in μ OR BP_{ND} changes from baseline PET (#1) session to follow-up PET (#2) session, 1 week after completion of HD-tDCS sessions that are inversely correlated with changes in mean clinical and experimental pain measures in chronic TMD subjects.

12.1.6 *Hypothesis #6*

TMD patients, compared to healthy controls, will be associated with reduction in μ OR BP_{ND} at the baseline level in the thalamus and other pain-related regions. The activation of μ OR neurotransmission, calculated as reductions in regional μ OR BP_{ND} during a sustained masseteric experimental pain challenge, will also be lower than the controls. Both these measures will be negatively correlated with clinical and experimental pain ratings. There will be no clinical trial with HD-tDCS involvement for this particular hypothesis. Hence, healthy subjects will not have stimulation and for TMD patients we will use the first, pretrial PET session (#1).

12.2 Sample Size Considerations

For the primary objective, a sample size of 24 in each group will have 80% power to detect group differences in change in VAS pain scores with an effect size of 1.2 using a 2-group t-test with a 0.05 two-sided significance level. Our sample size of 30 subjects per group is a conservative number that takes a 20% drop-out rate into consideration.

To demonstrate correlations between changes we observe in the μ OR BP_{ND} and changes in clinical and experimental measures of pain, we will be reporting correlation coefficients for baseline levels and change scores. With 60 subjects, the confidence intervals of these correlation coefficients will be reasonably narrow for 95% confidence in these estimates. For example, an observed Pearson product-moment correlation of $p = 0.8$ would have 95% confidence interval of (0.69, 0.88).

In addition, for secondary objectives 4 and 5 we will use the PET/MRI data from up to 12 healthy controls and 12 TMD patients who were recruited and scanned during the NIDCR-NIHR56 DE022637 project.

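### The primary power statement does not reproduce: at an effect size of 1.2, 24 per group gives 98% power, not 80%

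*Combined protocol and SAP*

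**What the plan says.** Section 12.2 (Sample Size Considerations) makes one power statement for the primary objective. For 24 subjects per arm it claims "80% power to detect group differences in change in VAS pain scores with an effect size of 1.2 using a 2-group t-test". The test is two-sided at the 5% level. The section then moves from 24 to the enrolled number: "Our sample size of 30 subjects per group is a conservative number that takes a 20% drop-out rate into consideration". Section 5.5.2 repeats the allowance: "The power calculations allow for a 20% dropout rate".

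The documents supplied do not say whether 1.2 is standardized or in VAS points. They give no SD for the change in VAS and no source for the 1.2. Section 12.3.2.1 names a mixed model for the primary outcome without an effect or a variance. Section 12.4 leaves the final analysis to a separate statistical analysis plan.

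**The concern.** The sentence fixes sample size, power, effect size, test and significance level. Any four of these determine the fifth, so it can be checked without outside information. An effect size of 1.2 SD is very large, and 24 per group is about twice what such an effect needs at 80% power. That suggests that one of the figures is wrong, or that 1.2 is a raw difference whose SD was left out.

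The two explanations point in opposite directions. If 1.2 is standardized, the trial has far more power for its stated target than it claims, and its real sensitivity (0.83 SD) is better than a reader would think. If 1.2 is in VAS points, power depends on an SD that the reader cannot see and could be well below 80%. Section 5.6 lists futility among the grounds for stopping the trial. A futility judgement, like the reading of a null result, needs a known target effect.

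**Working it through.** **Inputs, all from Section 12.2:** n = 24 evaluable per group, effect size 1.2, two-sample t-test, α = 0.05 two-sided, stated power 80%, drop-out 20%, 30 enrolled per group.

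**Formula.** With n per group and standardized difference d, the t statistic has 2n − 2 degrees of freedom and noncentrality δ = d·√(n/2). Power is the probability that |t| exceeds the two-sided 5% critical value. The figures below use the exact noncentral t distribution unless marked otherwise.

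**1. The plan's own figure, with d = 1.2 and n = 24.** δ = 1.2 × √12 = 4.157 and the critical value with 46 df is 2.013. Power is **98.3%**. The normal approximation gives Φ(4.157 − 1.960) = 98.6%. The stated 80% is not reproduced; the gap is about 18 percentage points.

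**2. Sample size for 80% power at d = 1.2.** The normal approximation gives 2 × (1.960 + 0.842)² / 1.2² = 10.9, i.e. 11 per group. The exact t calculation gives 11.94, i.e. **12 per group**. Check: n = 11 gives 76.3% and n = 12 gives 80.2%.

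**3. Effect detectable with 80% power.** With 24 per group, d = **0.826** (normal approximation: 2.802 × √(2/24) = 0.809). With all 30 per group, d = 0.736. At d = 1.2, 30 per group gives 99.5% power.

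**4. Other tests and significance levels at d = 1.2, n = 24.**

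| Variant | Power |
|---|---|
| One-sided 0.05 | 99.3% |
| Two-sided 0.01 | 92.4% |
| Bonferroni over the six hypotheses of Section 12.1 | 91.3% |
| Mann-Whitney at its worst-case efficiency (0.864) | 96.5% |

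None comes near 80%.

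**5. 1.2 read as VAS points.** For 80% power with 24 per group, the SD of the change must be 1.2 / 0.826 = **1.45**. The documents give no SD, so the SDs below are assumptions that show the range.

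| Assumed SD of change (points) | Power, 24 per group | Evaluable per group for 80% |
|---|---|---|
| 1.2 | 92% | 17 |
| 1.45 | 80% | 24 |
| 1.5 | 77% | 26 |
| 2.0 | 53% | 45 |
| 2.5 | 37% | 70 |
| 3.0 | 27% | 100 |

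**6. 24 read as a total.** Twelve per group gives 80.2% at d = 1.2. But the text says 24 in each group, and 12 / 0.8 = 15 does not lead to 30.

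**7. The rest of Section 12.2.** The drop-out step is right: 24 / (1 − 0.20) = 30. The interval for r = 0.8 with 60 subjects also reproduces: tanh(atanh 0.8 ± 1.96/√57) = (0.685, 0.876), against the stated (0.69, 0.88). Of the calculations in this section, only the primary power sentence fails.

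**The case against.** The best defence is that 1.2 is a difference in VAS points. With an SD of 1.45 every figure in the sentence then holds, and the fault is an omitted SD rather than a wrong calculation. This cannot be excluded, because the documents do not show which input is at fault. But an effect size given without unit or SD is ordinarily read as standardized. Nor can a unit be inferred from the scale: the VAS runs 0–10 in Sections 2.3.2 and 5.1 and 0–100 in Section 8.1.2. On this reading the statement still cannot be checked, because the quantity on which power depends is missing.

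Three further points limit the concern.

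- On the standardized reading the error understates power, so it does not show that 60 patients are too few.
- Section 12.2 also gives a precision argument for the correlations with 60 subjects. The power sentence is therefore the only justification for the primary comparison, not for every aim.
- The separate statistical analysis plan may contain the SD. That would help, but the protocol's own sentence should stand without it.

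It can also be said that 0.83 is only solved back from n = 24 and is no argument that 0.83 is the right target. That is correct. The figure describes what the trial can detect; the sponsor still has to say why that is the effect of interest.

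**Conclusion.** The statement is wrong as written and must be corrected. With 1.2 as a standardized effect, 24 per group gives 98.3% power rather than 80%, and 80% would need 12 per group. What 24 evaluable subjects per group detect with 80% power is 0.83 SD, whichever unit was intended for the 1.2. The stated 80% is recovered at 24 per group only if 1.2 is in VAS points and the SD of the change is about 1.45, which the documents supplied do not state. A slip between total and per-group numbers is the least likely explanation, because 24 per group leads to the 30 enrolled.

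These results assume a two-sample t-test on the change scores with equal groups, as the section specifies. The power values under the points reading rest on assumed SDs.

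**What to change.** The sponsor should first state whether 1.2 is standardized or in VAS points, and where it came from. Then replace the sentence in Section 12.2 with one that holds on either reading:

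> With 24 evaluable subjects per group, a two-sample t-test at the two-sided 0.05 level has 80% power for a standardized difference of 0.83 in the change in VAS score.

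Add why a difference of that size is of interest. If 1.2 was meant in points, name the scale, give the SD of the change (1.45 is needed for 80%) and its source, and show power over a range of SDs as in the table above. If 24 was really the total behind the calculation, say 12 per group and explain the 30 enrolled.

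The cost is one sentence, or a short paragraph if the points reading applies. Restating the figure needs no change in enrolment or in the drop-out allowance. If the sponsor's own SD turns out to be clearly above 1.45, the corrected text should report the lower power openly.
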